6.1.4.5. Time of birth relative to the transmission season

The transmission season period is defined:

- from April to September in the North hemisphere
- from October to March in the South hemisphere
- all year long in the tropical hemisphere

A summary of transmission season is displayed in the following table.

200150 (EPI-RSV-005 BOD)

				,
Statistical	Analysis	Plan	Amendment	1 Final

Country	Hemisphere	Transmission season period
Canada	North hemisphere	April 1 to September 30
United States	North hemisphere	April 1 to September 30
Finland	North hemisphere	April 1 to September 30
Argentina	South hemisphere	October 1 to March 31
South Africa	South hemisphere	October 1 to March 31
Thailand	Tropical hemisphere	All year long
Bangladesh	Tropical hemisphere	All year long
Honduras	Tropical hemisphere	All year long

Table 10Summary of transmission season by country

All subjects from tropical hemisphere will be considered to be born within the season.

Subjects from North hemisphere will be considered to be born within the season if they are born between April and September. Subjects from South hemisphere will be considered to be born within the season if they are born between October to March.

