6.6.3. Analysis of tertiary objectives: potential risk factors for RSV disease

For this objective, the analysis will be based on PPS.

The incidence, overall and by country, of first events of RSV-LRTI, RSV severe LRTI, RSV non severe LRTI (WHO definition) will be analysed using a Cox regression.

The following risk factors will be considered in the model:

- General:
 - Country of birth
 - Gender (as recorded in demography of extension phase)
 - Time of birth relative to the transmission season (see section 6.1.4.5)
- Characteristics at birth:
 - Gestational age at birth (see details section 6.1.4.1)
 - Birth weight (see details section 6.1.4.2)
 - Apgar at 5 mins of age (see details section 6.1.4.3)
 - Caesarian section
- Family history:
 - First degree relative with family history of asthma (see details section 6.1.4.4)
- Living environment and household composition:
 - Highest education level of the mother (see details section 6.1.4.6)
 - Highest education level of the father (see details section 6.1.4.6)
 - Number of people living in the household at month 3 (see details section 6.1.4.7)
200150 (EPI-RSV-005 BOD)

- Statistical Analysis Plan Amendment 1 Final
- Number of other children (<18 years old) living in the household at month 3 (see detail section 6.1.4.8)
- Subject in regular close contact with toddlers at month 3
- The child live in a surrounding where people smoke daily at month 3
- Breast feeding *

* Time dependent covariate; status is yes of subject ever breastfed from DOB until the end of breastfeeding given in the surveillance visit. Last day of month will be imputed for any partial date of breastfeeding end date.

As described in the section 11.1.5, covariates with univariate p-value less than 0.1 will be included in the multivariable model. The number of covariates included in the model will depend on the number of events (at least 10 events per covariates).

Please note that the multivariable model will be performed only if the number of events is sufficient (at least 10 events per covariates). In addition, depending on the data, other models could be explored or the model could be simplified.

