11. ANNEX 1 STANDARD DATA DERIVATION RULE AND STATISTICAL METHODS

11.1. Statistical Method References

11.1.1. Computation of incidence rates

For each endpoint, the incidence rate (IR, number of episodes/endpoints per 100 personyears) will be calculated by dividing the number of subjects reporting first episode over the follow-up period by the total person-year. A 95% CI will be computed using an exact method for a Poisson variable as described below.

The person-time at risk for an event of interest (e.g. RSV-LRTI) will be calculated as the time between the date of birth and the end of the at-risk period or the earliest of the followings:

200150 (EPI-RSV-005 BOD)

Statistical Analysis Plan Amendment 1 Final

- Date of first diagnosis of event of interest (e.g. first episode of RSV-LRTI);
- Date when child reaches 2 years;
- Date of last contact (lost-to follow-up, defined as no contact by the subject's parent(s)/LAR(s) over the period of 3 planned contacts and/or 2 months and after a final attempt has been made by mail. Once this has been reached, the subject is censored at the time of last contact);
- Date of death.

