11.1.5. Cox regression models

Cox regression models will be performed for the univariate analyses in order to obtain unadjusted hazards ratios of the determinants of interest.

200150 (EPI-RSV-005 BOD)

Statistical Analysis Plan Amendment 1 Final

In addition, a multivariable Cox regression model will be performed in order to estimate the relative contribution of each potential risk factor adjusting for the simultaneous effects of the other covariates. The model will include: time-independent covariates (e.g., country, gender etc.) and time-dependent covariates, breast feeding. Covariates selection will be done using statistical significance. Potential risk factors will be included in the multivariable models if univariate p-value will be less than 0.1.

The Table 15 details the time dependent status of the potential risk factors:

Table 15Time dependent status of the covariates

Potential risk factor	Time-dependent
Country of birth	No
Gender	No
Birth period	No
Gestational age at birth	No
Birth weight	No
Apgar at 5 mins of age	No
First degree relative with family history of asthma	No
Quartiles of cord blood maternal antibodies for RSV A	No
Quartiles of cord blood maternal antibodies for RSV B	No
Highest education level of the mother	No
Highest education level of the father	No
Number of people living in the household at month 3	No
Number of other children (<18 years old) living in the household at month 3	No
Subject in regular close contact with toddlers at month 3	No
The child live in a surrounding where people smoke daily at month 3	No
Breast feeding	Yes

Results from the multivariable Cox model will include hazards ratios (with 95% CI).

The number of covariates included in the model will depend on the number of events (at least 10 events per covariates).

Please note that the multivariable model will be performed only if the number of events is sufficient (at least 10 events per covariates). In addition, depending on the data other models could be explored or the model could be simplified.

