12.3.2. Secondary incidence analysis

12.3.2.1. (SO1) To determine the total health burden of non-RSV-associated RTI with a suspicion of involvement of the lower respiratory tract

Template 15 Incidence rate of first episode of [RTI with suspicion of involvement of LRT (all cause), WHO LTRI (all cause), WHO severe LRTI (all cause)], by age interval – overall and by country (PPS)

						95%	exact CI
Country	Age interval (Months)	Total number of subjects	Total number of first episode (all cause)	Total number of person- years	Incidence rate (100 person- years)	LL	UL
Overall	0-5						
	6-11						
	0-11						
	12-23						
	0-23						
<each country=""></each>							

Incidence rate computed using the number of first episode (all cause) as numerator and the total number of personyears over the age interval as denominator

CI=confidence interval, LL, UL for incidence = Exact 95% Lower and Upper confidence limits 95% CI computed using exact method for first episode incidence

Template 16 Monthly distribution of WHO RSV LRTI – by country (PPS)

	AR (N=)	BD	(N=)	CA	A (N=)	FI	(N=)	HN	(N=)	SA	(N=)	Tł	H (N=)	US	(N=)
Calendar Month	n	%	Ν	%	n	%	n	%	n	%	n	%	n	%	n	%
January																
February																
March																
April																
Мау																
June																
July																
August																
September																
October																
November																
December																

N=number of WHO RSV LRTI episode for each country

n (%) = total number and percent of WHO RSV LRTI episodes for each month

AR = Argentina

BD = Bangladesh

- CA = Canada
- FI = Finland

HN = Honduras

SA = South Africa

TH = Thailand

US = US

- 12.3.3. Tertiary incidence analysis
- 12.3.3.1. (TO5) To assess the impact of potential RSV risk factors (e.g. complications at birth, family history of respiratory disease, living environment and household composition, breast feeding, passive smoking, day care attendance) on the incidence and severity of RSV-associated LRTI.
- Template 17 Potential risk factors for first [WHO RSV LRTI WHO RSV severe LRTI] episode, evaluated in [Univariate – Multivariate] Cox model analysis for first [WHO RSV LRTI – WHO RSV severe LRTI] episode, over the 2 year follow-up period (PPS)

Characteristics	Category	Number of Observations		Hazard		Global n-
		model	Event	(95% CI)	p-value	value
RSV-A maternal antibodies levels in cord blood	Seronegative					
	Seropositive					
	Missing					

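### In the two-year risk-factor Cox model, birth season is a fixed covariate whose hazard ratio reverses with age, so its single hazard ratio has no useful meaning

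*SAP*

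**What the plan says.** SAP 6.6.3 states that the incidence "of first events of RSV-LRTI, RSV severe LRTI, RSV non severe LRTI (WHO definition) will be analysed using a Cox regression", overall and by country. Its covariate list includes "Time of birth relative to the transmission season (see section 6.1.4.5". Template 17 (SAP 12.3.3.1) presents the results "over the 2 year follow-up period (PPS", with birth in or out of season as a two-level factor.

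On covariate type, SAP 11.1.5 says: "The model will include: time-independent covariates (e.g., country, gender etc.) and time-dependent covariates, breast feeding". Table 15 marks birth period as not time-dependent. Covariates enter the multivariable model if the univariate p-value is below 0.1, subject to at least 10 events per covariate. Neither section specifies a proportional-hazards check, a season-by-age term or a current-season covariate. Both say that other models could be explored, depending on the data.

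For incidence rates, SAP 11.1.1 says that person-time "will be calculated as the time between the date of birth and the end of the at-risk period", ending at the latest on the "Date when child reaches 2 years".

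SAP 6.1.4.5 sets the season "from April to September in the North hemisphere", October to March in the South, and all year in Thailand, Bangladesh and Honduras, where every child counts as born in season. The protocol differs. Section 1.1.1 gives roughly October to March (North) and May to September (South). The Appendix C recruitment figure assumes November to April and May to October.

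**The concern.** Follow-up covers two full annual cycles. Birth season therefore sets the age at which a child meets RSV, not how many seasons the child meets. The contrast between children born in and out of season changes sign as they age, and one hazard ratio for 24 months cannot describe that.

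At stake is the season row of Template 17. A reader could take a value near 1 as absence of a seasonal effect, or a value below 1 as protection from in-season birth, when either can arise from the same strong seasonality. The p<0.1 screen then acts on that number.

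**Working it through.** The plan gives no hazard ratio, event count or power for this model, so there is no figure to reproduce.

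**Inputs from the documents.** Births spread evenly over the year (protocol Appendix C aims at stable monthly recruitment). Age pattern from protocol Table 12, rows 44.1/15.0/3.7 and 16.9/5.1/2.7 per 1000 child-years at 0–5/6–11/12–23 months. LRTI rate 8 times the hospitalization rate, and 20% drop-out (protocol 9.3).

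**Assumptions.** Age is the Cox time axis, as for person-time in SAP 11.1.1. The season lasts six months. The in-season to off-season rate ratio R is 2, 5 or 10; the documents give no such ratio.

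**Step 1: hazard ratio by age, coded and actual seasons aligned.** Let f be the average share of in-season-born children who are in season during an age band. The share among off-season-born children is 1−f. Over 0–3, 3–6, 6–9 and 9–12 months, f = 0.75, 0.25, 0.25, 0.75. Ignoring depletion by earlier events:

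HR = [1 + f(R−1)] / [1 + (1−f)(R−1)]

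| R | 0–3 and 9–12 months | 3–6 and 6–9 months |
|---|---|---|
| 2 | 1.75/1.25 = 1.40 | 1.25/1.75 = 0.71 |
| 5 | 4/2 = 2.00 | 2/4 = 0.50 |
| 10 | 7.75/3.25 = 2.38 | 3.25/7.75 = 0.42 |

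The pattern repeats in year 2. Allowing for depletion, drop-out and the Table 12 patterns changes little: for R=5, 2.01–2.19 at 0–3 months and 0.50–0.54 at 3–6.

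**Step 2: SAP northern coding (April–September) against an actual season of November–April.** The same averaging gives f = 2.5/18, 10.5/18, 15.5/18 and 7.5/18. For R=5 the hazard ratios are 1.556/4.444 = 0.35, 3.333/2.667 = 1.25, 4.444/1.556 = 2.86 and 2.667/3.333 = 0.80. They still cross 1, at different ages.

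**Step 3: the single 24-month hazard ratio, seasonal countries only.** This solves the expected Cox score for the fixed covariate, with a flat hazard, a step hazard following Table 12, and a log-linear decline through Table 12.

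| Actual season | Flat | Table 12 patterns |
|---|---|---|
| Same as coded | 1.00 | steps 1.00–1.03; log-linear 1.09–1.17 (R=5), 1.11–1.21 (R=10) |
| North, November–April | 0.98 | 0.72–0.84 (R=5), 0.66–0.81 (R=10) |
| North, October–March | 1.00 | steps 0.97–1.00; log-linear 0.83–0.88 |
| South, May–September | 0.99 | 0.71–0.88 |

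With R=2 the aligned range is 1.00–1.09, and the November–April values rise to at most 0.91.

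**Step 4: the screen.** In simulated cohorts of 1,500 children from seasonal countries, with seasons aligned and R=5 or 10, birth season reached p<0.1 in 4–13% of cohorts with step hazards and 21–47% with log-linear hazards.

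**Step 5: overall univariate fit.** Assume eight countries of equal size. The in-season group is then three tropical countries plus half of five temperate ones, and the off-season group is the other half. If the tropical rate is k times the temperate rate and birth season has no net effect, the crude ratio is (3k + 2.5)/5.5: 0.73, 1.00 and 1.55 for k = 0.5, 1 and 2. A Cox calculation with R=10 and the Table 12 steps gave 0.74, 1.07 and 1.51.

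**Step 6: a correctly dated current-season indicator.** On simulated data it recovered R: median 4.7–5.4 for R=5 and 8.6–11.2 for R=10. The fixed birth-season term gave 1.02–1.20 on the same settings.

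**The case against.** Birth season is settled at birth, so Table 15 is literally correct, and breastfeeding, which does change, is not a precedent. If birth season does not alter two-year risk, a ratio near 1 answers that question fairly. This stands as far as it goes. But the result is not reliably near 1; Step 3 shows that it moves with the season dates and the age gradient.

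Seasonality is also reported elsewhere. Template 12 gives first-six-month incidence by time spent in season, Template 16 gives cases by calendar month, and the cord-blood Cox models (SAP 6.9.1) run over 0–2 and 0–5 months with time of birth as a possible covariate. This lowers the stakes but does not repair Template 17, and the 0–5 month model still spans the reversal at about three months.

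The reversal does not apply to the three tropical countries, which have no contrast. The mixing in Step 5 concerns the overall univariate fit; a model that includes country, or a fit by country, avoids it.

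A reader might infer that the other hazard ratios are biased because season is poorly modelled. The documents do not support that. Steady monthly recruitment should leave season roughly independent of the other factors, and a check with season omitted returned 1.53 and 1.44 for a baseline factor with true ratio 1.5 (standard error about 0.03 on the log scale).

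**Conclusion.** The point holds for the five seasonal countries. The birth-season hazard ratio reverses with age even at an assumed 2-fold season, so proportional hazards fails and the two-year figure describes no age period. Its likely value is about 1.0–1.2 if coded and actual seasons coincide, and about 0.7–0.9 under Appendix C's northern dates against the SAP coding. Both ranges rest on the Table 12 age patterns, even births, a six-month season and assumed ratios of 2 to 10. The screen may therefore keep or drop the term for the wrong reason.

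A reader might infer that the ratio must average to 1 whichever months define the season. Only the reversal is that general; the average depends on alignment and on how fast risk falls with age. The analysis is tertiary and descriptive, and no primary incidence estimate changes.

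**What to change.** First reconcile the season months in SAP 6.1.4.5 and Table 10, and in the template footnotes that repeat them, with protocol 1.1.1 and Appendix C. This must come first: where the coded season is the opposite of the actual one, a current-season indicator would return about 1/R (0.2 for 5-fold, 0.1 for 10-fold).

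Then, in SAP 6.6.3, Table 15 and Template 17, do one of the following:
- replace the single two-year ratio with birth season by age period, at least 0–2 and 3–5 months; or
- add a time-dependent indicator that the child is currently in the country's transmission season.

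Estimate the term within country or stratified by country, stating that the three tropical countries contribute no contrast. Keep it in the multivariable model whatever its univariate p-value, and add a proportional-hazards check.

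The cost is SAP wording, a little programming and a few more parameters, which count toward the rule of 10 events per covariate. No new data are needed: the dates are held, and one time-dependent covariate is already planned.

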6.5.7. Collection of medical history, demographic and lifestyle characteristics

Obtain the family medical history, demographic and lifestyle characteristics of the subject as required by the eCRF, by interviewing parent(s)/LAR(s) and/or reviewing the medical records and record data collected in the subject's eCRF. This includes family history of respiratory disease, living environment and household composition, breastfeeding, passive smoking and day-care attendance.

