6.5.13. Recording of data on changes to baseline medical and demographic data

On a quarterly basis, the investigator/study staff should expand a regular surveillance contact by asking the parents/LARs for changes to the baseline medical, demographic and lifestyle characteristics data collected at Visit 2. This includes at least;

- diagnosis of chronic diseases
- medical events requiring hospitalization
- vaccinations received (on disease level, not full vaccination details)
- start/stop attendance of day-care and other changes in daily care
- start/stop breastfeeding
- changes to household composition and/or living conditions

This data will be recorded in a quarterly surveillance eCRF.

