The measured maternal antibody levels by storage condition or tube type will be analysed graphically and by group statistics (mean, 95% CI). Group means will be compared by t-test to assess the statistical significance of differences.

The measured maternal antibody levels in samples collected 'according to recommended procedure' and 'not according to recommended procedure' will be analysed graphically and by group statistics (mean, 95% CI). Group means will be compared by t-test to assess the statistical significance of any difference.

• To assess the impact of potential RSV risk factors (e.g. complications at birth, family history of respiratory disease, lifestyle characteristics and household composition, breast feeding, passive smoking, day care attendance) on the incidence and severity of RSV-associated LRTI.

The incidence of any, severe, non-severe RSV-associated LRTI will be analysed using a Poisson regression model including potential risk factors.

• To assess the natural decay of maternal antibody levels using a single follow-up blood sample collected from a randomly selected sub-cohort of subjects at 2, 4, 6, 12, 18 and 24 months.

The primary analysis will be based on ATP sub-cohort for this objective.

The decay of maternal antibody levels over time will be analysed graphically and by a log-linear regression. A true, natural decay curve will be explored by stochastically reducing the sample to uninfected subjects only. The following steps will be taken to identify, confirmed and suspected infected subjects to eliminate these from the sample;

- Subjects with an RSV positive nasal swab during the study before time of sampling will be eliminated.
- A sensitivity analysis of the decay curve will be explored in sub-sample consisting of the subjects born 'off-season' as these have the lowest likelihood of having been infected.
- Subjects with an antibody titer at the sampling time that is more than 2-fold above the expected value based on their baseline (cord blood) value and the established decay curve will be considered to have been infected, eliminated and the decay curve refined.
- Step 3 is repeated up to 5 times until the most accurate decay curve is established.

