3.3. Tertiary objectives

In a cohort of infants followed-up from birth up to 2 years of age;

- To explore the association of co-infections with the incidence of RSV-associated LRTI and/or severe LRTI (as determined by the LRTI case definition and severity scale) using xTAGTM respiratory viral panel (RVP) fast assay.
- To explore the association of RSV and other respiratory viruses with the incidence of LRTI and/or severe LRTI (as determined by the LRTI case definition and severity scale) using xTAGTM RVP Fast assay.
- To explore the association of RSV viral load with the incidence of RSV-associated RTI, LRTI and/or severe LRTI (as determined by the LRTI case definition and severity scale).
- To explore the impact of changes to the symptoms and threshold levels of symptoms in the LRTI case definition and severity scale.

200150 (EPI-RSV-005 BOD)

Statistical Analysis Plan Amendment 1 Final

- To assess the impact of potential RSV risk factors (e.g. complications at birth, family history of respiratory disease, living environment and household composition, breast feeding, passive smoking, day care attendance) on the incidence and severity of RSV-associated LRTI.
- To explore the impact of variations in cord-blood sample collection variables on the stability of test results.
- To assess the natural decay of maternal antibody levels using a single follow-up blood sample collected from a randomly selected sub-cohort of subjects at 2, 4, 6, 12, 18 and 24 months.

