4.3. Tertiary endpoints

- Occurrence of RSV and other respiratory viruses as confirmed by xTAG[™] RVP Fast assay:
 - Parainfluenza virus type 1, 2, 3, and 4
 - Human Metapneumovirus
 - Rhinovirus
 - Adenovirus
 - Bocavirus

- Coronavirus 229E, OC43, NL63, HKU1
- RSV
- Influenza A, including subtypes H1 and H3
- Influenza B
- RSV viral load as determined by RSV RT-qPCR.
- Occurrence of any symptom identified in cases of potential LRTI.
- Cord-blood sample collection variables including collection and storage times and temperatures.
- Occurrence of potential risk factors including complications at birth, family history of respiratory disease, living environment and household composition, breastfeeding, passive smoking and day-care attendance.

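### Day-care attendance is a named and collected risk factor for RSV LRTI, but the pre-specified Cox analysis (SAP 6.6.3, Table 15, Template 17) leaves it out without saying so.

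*SAP*

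**What the plan says.** The target is stated twice. The tertiary objective in SAP 3.3, which matches protocol 2.1.3, is to assess potential risk factors, with examples ending "breast feeding, passive smoking, day care attendance) on the incidence and severity of RSV-associated LRTI". The tertiary endpoints in SAP 4.3, which match protocol 9.1.3, list "breastfeeding, passive smoking and day-care attendance" among the factors whose occurrence is an endpoint.

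The data are to be collected. Protocol 6.5.7 describes the baseline record at Visit 2: "This includes family history of respiratory disease, living environment and household composition, breastfeeding, passive smoking and day-care attendance". Protocol 6.5.13 adds quarterly questions on changes, including "start/stop attendance of day-care and other changes in daily care".

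The analysis narrows between the documents. Protocol 9.7.3 says: "The incidence of any, severe, non-severe RSV-associated LRTI will be analysed using a Poisson regression model including potential risk factors". It names no separate covariate list, so the factors are those of the objective it answers. SAP 6.6.3 replaces this with a Cox model and a closed list, introduced by "The following risk factors will be considered in the model". Day-care is not on that list. The closest item is "Subject in regular close contact with toddlers at month 3". SAP 11.1.5 describes the time-varying part of the model as "time-dependent covariates, breast feeding", and Table 15 marks every other covariate as fixed.

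**The concern.** The objective, the endpoint and the data collection all point to an estimate for day-care, and the analysis section does not produce one. A reader of the report would find the factor promised in the objective and missing from the results. Any later day-care analysis would be post hoc, because nothing in the plan fixes how the exposure is defined.

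Toddler contact does not fill the gap. Template 17 covers the full two years, so a child who starts day-care at 6, 12 or 18 months keeps the month-3 code throughout. By its wording the item is also about contact with toddlers, wherever that happens, and not about attendance.

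**Working it through.** The plan gives no figure on this point, so the main check sets the sections side by side.

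- Objective (SAP 3.3): day-care named.
- Endpoint (SAP 4.3): day-care named.
- Collection (protocol 6.5.7 and 6.5.13): recorded at Visit 2, changes asked quarterly.
- Cox list (SAP 6.6.3): 15 covariates, namely country, gender, season of birth, gestational age, birth weight, Apgar, caesarean section, family asthma, mother's education, father's education, household size, other children, toddler contact, smoking and breastfeeding. No day-care.
- Table 15 (SAP 11.1.5): no day-care.
- Template 17 (SAP 12.3.3.1): no day-care row, although the heading above it repeats the objective and still names day-care.
- Baseline summary (Template 4): no day-care row.
- Declared changes (SAP section 9): the move from Poisson to Cox is declared for this analysis; dropping day-care is not.

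Breastfeeding is the useful comparison. Its start and stop are asked in the same quarterly list as day-care, and the SAP turns it into a time-dependent covariate. The same kind of information on day-care is not used.

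**Cost in events.** The SAP wants ten events for each covariate in the multivariable model.

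- By covariate, if all 15 entered: 15 × 10 = 150 events. With day-care: 16 × 10 = 160.
- By parameter: 8 countries use 7; Apgar, household size and number of children use 2 each; the other 11 covariates use 1 each. That is 7 + 6 + 11 = 24, or 240 events. With day-care: 25 × 10 = 250.
- Table 15 and Template 17 also carry RSV-A and RSV-B cord-blood terms. Counting them as quartiles gives 17 covariates (170 events) or 24 + 2 × 3 = 30 parameters (300 events). With day-care these become 180 and 310.

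The increment is 10 events on every count.

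**Are the events likely to be there?** Protocol 9.3 takes a first-year RSV LRTI hospitalization rate h of 10 to 50 per 1000 child-years and expects all RSV LRTI to be 8 times as frequent. Protocol 5.1 expects about 1920 evaluable children. Assuming a constant hazard and a full first year for all of them, first RSV LRTIs in year 1 = 1920 × (1 − exp(−8h)):

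- h = 0.010: 1920 × (1 − exp(−0.08)) = 148
- h = 0.020: 1920 × (1 − exp(−0.16)) = 284
- h = 0.030: 1920 × (1 − exp(−0.24)) = 410
- h = 0.040: 1920 × (1 − exp(−0.32)) = 526
- h = 0.050: 1920 × (1 − exp(−0.40)) = 633

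At the lowest rate, year 1 alone falls just short of the 150 needed for the present list. From 20 per 1000 upward it covers 160, 180 and 250. From 30 upward it covers 310. Second-year events would add to this, and screening at p < 0.1 would shorten the list. The documents give no expected rate for severe LRTI, so that model cannot be checked.

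**The case against.** The best case for leaving the plan alone has four parts.

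*The SAP is flexible.* Section 6.6.3 allows alternative or simpler models depending on the data, and protocol 9.10 allows modified analyses if the report justifies them. A reader might infer from the omission that day-care can never be assessed; the documents do not support that. What stands is narrower: these clauses name no covariate, so day-care has no pre-specified analysis.

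*The harm to other estimates is unproven.* A reader might infer that the hazard ratios for siblings, breastfeeding or parental education are left confounded. The documents give no association between day-care and those factors or the outcome. Day-care may lie on the pathway from parental education to infection, in which case adjusting for it changes the effect being estimated and does not remove a bias. The p < 0.1 screen also means that adjustment is not assured even after the fix.

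*The cord-blood models lack the term too.* That is true of Templates 43 to 45, but they cover only 0–2 and 0–5 months and serve an objective that does not name day-care. The argument from later entry does not reach them.

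*The data may be incomplete.* Protocol 6.5.13 does not say that dates are recorded, and the eCRF is not among the documents. Appendix E lets contacts be cancelled and active surveillance be suspended. Visit 2 falls within 5 working days of birth, so its value says little about exposure. Complete start and stop data for every child therefore cannot be assumed. The wording of the toddler question is also unknown, so it may capture some group care at month 3. It still cannot capture later entry.

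The objective's list is introduced as examples, but the endpoint includes day-care outright, so that does not excuse the omission.

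**Conclusion.** The point holds as an undeclared omission from the pre-specified risk-factor analysis in SAP 6.6.3, Table 15 and Template 17. Its size is one named risk factor without an estimate, in one tertiary objective, within analyses that the SAP calls descriptive. No incidence, co-primary or secondary result depends on it. The size of any effect on the other hazard ratios cannot be derived from the documents, and none should be claimed.

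It should be corrected because the factor is an endpoint, the plan already collects information on it, and the SAP already handles breastfeeding in a comparable way. The conclusion about the omission rests on the text alone. The conclusion that the fix is affordable rests on the protocol's rate assumptions and a constant first-year hazard, for RSV LRTI only. It also needs the eCRF to hold usable day-care status at the quarterly contacts.

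**What to change.** Add day-care attendance to SAP 6.6.3, Table 15 and Template 17 as a time-dependent yes/no covariate: Visit 2 status, updated from the quarterly start/stop records. Keep the p < 0.1 screen and the ten-events rule.

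The breastfeeding rule handles one end date and cannot simply be copied, so state in advance how to treat:

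- repeated starts and stops;
- changes between two contacts, including whether status is taken as last known before the event so that withdrawal because of illness does not recode the exposure;
- missed, cancelled or suspended contacts;
- partial or absent dates, after checking what the eCRF records.

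If day-care was dropped on purpose, section 9 should say so and give the reason. That would make the plan consistent but would still leave the named factor without an estimate.

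The cost is some derivation programming, one more candidate covariate and, if it enters the multivariable model, 10 more events under the SAP's rule. No collection beyond what the protocol already specifies is proposed, and Templates 43 to 45 stay as they are.
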